C. Inclusion Criteria

- Male or Female - ages 18-65 years of age inclusive
- Current diagnosis of Major Depressive Disorder based on DSM-IV criteria

- Able to understand study rules and procedures and willing to sign written informed consent for study participation
- Inadequate response to antidepressants: having a score of ≥ 14 on the 17-item HAMD and not having a $\geq 50\%$ reduction in HAMD or CGI-S scores from baseline after a retrospective confirmation of an adequate trial of a single antidepressant (defined as a minimum 6-week trial of acceptable therapeutic dose (daily dose ≥ 40 mg of fluoxetine, 40 mg of paroxetine, 20 mg of citalopram, 10 mg of escitalopram, 37.5 mg of paroxetine CR, 150 mg of sertraline, 100 mg of fluvoxamine).

If female, nonpregnant/nonlactating status

- Duration of current MDD ≥ 4 weeks and < 24 months
Not more than 2 treatment failures of adequate antidepressant trials for current episode of MDD

D. Exclusion Criteria

- Has previously participated in a levomilnacipran ER or quetiapine XR or quetiapine clinical study in previous 12 months
- Has 1 or more the following: Current or past history of: manic or hypomanic episode, schizophrenia or any other psychotic disorder defined in the DSM- 5
- Diagnosis of alcohol or other substance use disorder (except nicotine and caffeine) as defined in the DSM-5 that has not been in sustained full remission for at least 6 months prior to screening (participant must also have negative urine drug screen prior to baseline).
- Presence or history of a clinically significant neurological disorder (including epilepsy)
- Poorly controlled Hypertension or Diabetes
- uncontrolled narrow-angle glaucoma
- hypersensitivity to levomilnacipran, milnacipran , quetiapine or quetiapine XR
- Neurodegenerative disorder.
- Has a thyroid stimulating hormone value outside the normal range at the Screening Visit that is deemed clinically significant by the investigator.

- Has clinically significant abnormal vital signs as determined by the investigator.
- Has a clinical significant abnormal electrocardiogram.
- Has screening laboratory values greater than 2.5 times the upper or lower limits of normal range or judged to be clinically significant

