This is an 8-week trial with a 1 week (week 9) safety follow up visit. Visits will be planned to occur at the screening visit and weeks 0, 1, 2, 3, 4, 6, 8 and 9.

The following activities and/or assessments will be performed at/during the Screening visit (Week -4 to Week 0):

- Obtain written informed consent prior to performing any of the formal screening procedures.
- Administer the M.I.N.I
- Administer the C-SSRS, MADRS, ASEX, HAM-D, HAM-A, DSST, CGI-S, RVLTL, Spontaneous Reported AEs and Sheehan Disability
- Record demographic information
- Obtain medical and surgical and psychiatric history
- Record prior and concomitant medications
- Record vital signs (temperature, heart rate, supine and orthostatic blood pressure), body height and body weight
- Perform a complete physical examination
- Perform a 12-lead ECG

- Collect blood and urine samples for evaluation of standard laboratory safety test (chemistry, hematology, and urinalysis)
- Assess all applicable inclusion and exclusion criteria
- Schedule the baseline visit for those subjects that do not require washout of prohibited medications
- Subjects requiring washout of prohibited medication will be provided washout requirements
 - Subjects in adjunctive quetiapine arm will be permitted to continue their pre-existing antidepressants if FDA approved for depression; if not FDA approved, they will be switched to an FDA approved medication for the duration of the study but will undergo washout of other prohibited medications
- Provide instructions on washout of prohibited medication(s), including the duration of the washout period (if needed)
- Assess for and record AEs and concomitant medications

Once potential eligibility is confirmed, the investigator, or a person designated by the investigator, will contact the subject by telephone at or during the Randomization/Baseline (Week 0):

- Determine appropriate duration of the washout period of prohibited medication(s), taking into account any labeling requirements for tapering of medication dose(s), as well as the minimal washout requirements

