 - Weekly phone calls will include a Symptom Checklist, consistent with symptoms of Major Depression, suicidal risk and adverse events, which the Study Coordinator will review with the subject. Any potential concerns will be reviewed with the subject. Any potential concerns will be discussed with the PI and appropriate interventions for subject safety will be planned. The same symptom checklist and monitoring plan for the subjects will be used at the Duke and the non-Duke site.
- Assess all applicable inclusion and exclusion criteria

- Administer the C-SSRS, MADRS, ASEX, HAM-A, DSST, CGI-S, RVLTL, AES, Spontaneous Reported AEs and Sheehan Disability
- Assess for and record AEs and concomitant medications
- Dispense study medication

The following activities and/or assessments will be performed at Weeks 1 through Weeks 6:

- Assess for and record AEs and concomitant medications
- Administer the C-SSRS, MADRS, ASEX, HAM-A, DSST, CGI-S, RVLTL, AES, Spontaneous Reported AEs and Sheehan Disability
- Collect study medication and review medication compliance
- Dispense study medication

The following activities and/or assessments will be performed at Week 8: End of Study or Early Termination:

- Assess for and record AEs and concomitant medications
- Collect study medication and review medication compliance
- Record vital signs (temperature, heart rate, supine and orthostatic blood pressure), and body weight
- Collect blood and urine samples for evaluation of standard laboratory safety tests
- Administer the C-SSRS, MADRS, ASEX, HAM-A, DSST, CGI-S, RVLTL, AES, Spontaneous Reported AEs and Sheehan Disability
- Perform a 12-lead ECG

The following activities and/or assessments will be performed at the Week 9/ Safety Follow-Up Visit:

- Assess for and record AEs and concomitant medications
- Administer the C-SSRS, Spontaneous Reported AEs and the DSST

After all study assessments has been completed or if the participant completes an early term visit, the participants will be referred back to their outpatient treating physician for

psychiatric care. Participants who are uninsured will be referred to Lincoln Community Health Center or Durham Access. Results of the subject's participation will not be available to the subject before they return to their treating doctor.

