Patient termination will occur if the patient experiences a clinically significant worsening of MADRS scores in two successive visits or any worsening on CSSRS on two consecutive visits, or based on clinician judgment or patient preference.

D. Concomitant Medications and Therapy:

All medications for pre-existing medical conditions will be permitted to continue unchanged provided subjects are on a stable dose of at least 12 weeks. Subjects on prohibited concomitant mood stabilizers or atypical antipsychotics will require a 2-4-week washout of the prohibited medication after the subject meets all eligibility criteria at the screening visit. Washout of prohibited medication will be determined by the $\frac{1}{2}$ life of the drug. Subjects on a minimum of 3 months of stable dose of hypnotics (e.g. zolpidem 10 mg per day or benzodiazepine dose of ≤ 2 mg per day of lorazepam or trazodone ≤ 100 mg per day) will be allowed to continue their hypnotic medication at the same dose. Over the counter medications will be permitted if in the opinion of the investigator, they are not considered to have any significant impact on the study. Any medication that has the potential to cause a clinical significant drug interaction with levomilnacipran ER or quetiapine in the judgment of the investigator will require a washout.

VI. STUDY MEDICATION

A. Description and Dispensing

a. Description and Dispensing

Levomilnacipran and quetiapine will be dispensed/administered at specified study visits.

b. Storage

All study medications will be stored in a double-locked cabinet in the Civitan Building. With available access only to the study investigator and research coordinator.

VII. CLINICAL ASSESSMENTS

Diagnostic Evaluation: The Mini-International Neuropsychiatric Interview (MINI) (version 6.6) for DSM-5 Axis I Disorders to establish diagnosis.

Study Parameters/Efficacy:

Efficacy:

The primary outcome measure will be:

Change from Baseline to end of treatment in Montgomery-Åsberg Depression Rating Scale (MADRS) Total Score.

Secondary outcome will be:

Change from baseline to end of treatment in
Clinical Global Impression Scale- Severity (CGI-S) and Improvement (CGI-I) scores
Hamilton Anxiety Rating Scale (HAM-A) scores
Hamilton Depression Rating Scale (HAM-D) scores
Sheehan Disability Scale (SDS) total score.
Scores on Digit symbol substitution test (DSST)
Scores on Rey's Verbal Learning Test (RVLT).
Scores on Apathy Evaluation Scale (AES).

Safety/Tolerability:

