Primary efficacy analysis will be conducted in the ITT population using the last-observation-carried-forward (LOCF) method. Treatment group comparisons will base on changes in MADRS from baseline to week 8/end of treatment from repeated measures ANOVA or analysis-of-covariance (ANCOVA) model containing treatment site, gender and baseline MADRS score included as a covariate.

Secondary efficacy analysis: Repeated measures ANOVA or ANCOVA models will be used to analyze change from baseline in secondary measures. Response and remission rates at end of treatment will be compared using the Cochran-Mantel- Haenszel test. No formal hypothesis testing will be performed on safety data. Safety outcomes will be summarized by treatment group and study visit (observed cases) using descriptive statistics. Any clinically significant findings among patients who terminated early will be discussed separately. All analyses will be conducted using SAS Version 9.1.3 (SAS Institute, Inc.; Cary, North Carolina). Statistical comparisons of efficacy outcomes will be 2-sided and considered significant at $P < .05$. Comparisons for secondary endpoints will be not adjusted for multiplicity.

D. Definition of Evaluable Subject (Safety and Efficacy)

Subjects will be defined as able to be evaluated by two methods. The primary method will be an intent-to-treat analysis, including those who discontinue drug due to lack of efficacy or due to side effects. The secondary method will be completer analysis.

XI: ETHICAL AND REGULATORY CONSIDERATIONS

A. Institutional Committee Approval

Duke University Health Systems Institutional Review Board (DUHS IRB) will need to approve the protocol at the Duke site. [name] site will use an external IRB (e.g. Copernicus, Western) and provide Duke with a copy of its approval.

B. Informed Consent

Participation in this study is voluntary and at no cost to the subjects. All potential participants interested in this study must be thoroughly informed of the details of the study. Prior to study participation in this trial, each subject will have an opportunity to ask questions and will sign an approved informed consent form. The signed consent forms will be filed with the investigator's copies of the Case Report Forms for each subject and a copy provided to the subject. Any subject may voluntarily withdraw from the study at any time without prejudicing treatment.

C. Document Storage and Retention

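### Change in HAM-D is a declared secondary outcome, but no HAM-D is scheduled after screening, so no change score can be computed.

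*Combined protocol and SAP*

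**What the plan says.** **Outcome.** Section VII (Clinical Assessments) gives the secondary outcomes as changes from baseline to the end of treatment. The list includes "Hamilton Depression Rating Scale (HAM-D) scores".

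**Analysis.** Section VII.C (Plan of Data analysis, within Statistical Evaluation) states: "Repeated measures ANOVA or ANCOVA models will be used to analyze change from baseline in secondary measures". HAM-D is not named there, but it is on the list that the sentence covers.

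**Visits.** Section V.C states: "Visits will be planned to occur at the screening visit and weeks 0, 1, 2, 3, 4, 6, 8 and 9".

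**Assessments in the visit text (section V.C).** The screening list includes HAM-D: "Administer the C-SSRS, MADRS, ASEX, HAM-D, HAM-A, DSST, CGI-S, RVLTL". The lists for Week 0, Weeks 1 to 6 and Week 8/early termination are identical to one another and omit it: "Administer the C-SSRS, MADRS, ASEX, HAM-A, DSST, CGI-S, RVLTL, AES, Spontaneous Reported AEs and Sheehan Disability". The Week 9 list also omits it: "Administer the C-SSRS, Spontaneous Reported AEs and the DSST".

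**Assessments in the schedule (section XIV).** The HAM-D row has one mark, in the screening column.

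**Other use of HAM-D.** Section IV.C uses the scale for entry, requiring a minimum score "on the 17-item HAMD and not having a" 50% or greater reduction on the existing antidepressant.

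**The concern.** A change score needs a baseline value and a later value. The plan schedules one HAM-D rating per participant, before treatment starts, so the later value does not exist. The outcome list and the visit plan cannot both stand.

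This goes beyond missing detail, because a site that follows either the visit text or the schedule exactly will not collect the data that a declared outcome needs. Ratings that were not taken cannot be recovered later. The report would then have to drop the outcome, or explain its absence after the results are known. The plan would also lose its second clinician-rated depression scale, the natural cross-check on MADRS.

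**Working it through.** The plan gives no figure to reproduce. The check is a count of scheduled HAM-D ratings, made separately in the visit text and in the schedule.

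**Planned visits (section V.C).** Screening and Weeks 0, 1, 2, 3, 4, 6, 8 and 9: 1 + 8 = 9 visits. From Week 1 to Week 8 there are 6 (Weeks 1, 2, 3, 4, 6 and 8).

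| Visit | HAM-D, visit text | HAM-D, schedule | MADRS and HAM-A, both sources |
|---|---|---|---|
| Screening | 1 of 1 | 1 of 1 | 1 of 1 |
| Week 0 | 0 of 1 | 0 of 1 | 1 of 1 |
| Weeks 1, 2, 3, 4, 6, 8 | 0 of 6 | 0 of 6 | 6 of 6 |
| Week 9 | 0 of 1 | 0 of 1 | 0 of 1 |
| Total | 1 of 9 | 1 of 9 | 8 of 9 |

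**Is this a damaged table?** The visit text and the schedule differ on other items; for example, the Week 9 DSST is in the visit text only. They agree on HAM-D. Schedule rows with blank cells in the middle, such as ECG and vital signs, keep their column positions. A lost table mark would not explain the gap.

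**Is HAM-D alone in this?** Section VII lists 8 secondary scores: CGI-S, CGI-I, HAM-A, HAM-D, SDS, DSST, RVLT and AES. CGI-I is absent from the visit text but is in the schedule. AES is absent from the schedule as shown but is in the visit text. CGI-S, HAM-A, SDS, DSST and RVLT are in both after screening. HAM-D is the only one of the 8 with no rating after screening in either source.

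**Can another rule supply the value?**

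- Carrying the last observation forward is stated for the primary analysis. Applied to HAM-D, it would carry the screening value, giving screening minus screening = 0 for everyone.
- Eligibility is assessed again at Week 0, which might prompt a repeat HAM-D because a minimum score is an entry criterion. No repeat is listed, and one would still leave no end-of-treatment value.

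**Result.** HAM-D ratings per participant after the start of treatment: 0. Participants able to supply a change score: 0 of 60.

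**Ratings needed to close the gap (upper bounds, before dropout).** One visit: 1 × 60 = 60. Two visits: 2 × 60 = 120.

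**The case against.** The strongest reply is that little is lost:

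- MADRS is the primary outcome, and it already measures depression severity at every visit through Week 8.
- Secondary comparisons are not adjusted for multiplicity, and the sample size does not rest on HAM-D.
- Two separately laid out sources agree on screening only, so HAM-D may have been meant for eligibility alone, with the slip in the outcome list.
- The analysis sentence never names HAM-D.
- Week 0 is labelled the baseline visit, and the eligibility re-check there could imply a rating.
- Weeks 1 to 6 and Week 9 are not needed for a change to the end of treatment.

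Much of this is fair. The impact is confined to one secondary outcome, and the rating that matters most is the one at Week 8/early termination. The documents cannot settle intent: the three identical assessment lines could equally reflect a copying slip.

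None of it removes the contradiction. HAM-D falls under the analysis sentence through the outcome list. A Week 0 rating, implied or not, gives no end-of-treatment value. If HAM-D was meant for eligibility only, the outcome list is wrong and needs correcting.

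**Conclusion.** The concern holds. HAM-D is scheduled at 1 of 9 visits and at none from Week 0 onward, so 1 of the 8 declared secondary scores cannot be analysed as planned. This assumes only that sites follow the visit text or the schedule as written; extra ratings outside the plan are not counted. It does not depend on which document section reflects the intent. The primary MADRS outcome and the sample size are unaffected. It should be fixed because the contradiction is clear and the correction is cheap, but it does not threaten the trial's main conclusion.

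**What to change.** Choose one of the following.

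1. **Remove HAM-D from the secondary outcomes** and keep it for eligibility only. This is a change of wording. The cost is having no second depression scale as a cross-check on MADRS.
2. **Add HAM-D at Week 8/early termination** in both the visit text and the schedule. Name the screening value as its baseline, and specify ANCOVA of the Week 8/early termination value with that baseline as covariate. This adds at most 60 ratings at an existing visit. The cost is a HAM-D baseline from a different visit than the MADRS baseline.
3. **Add HAM-D at Week 0 and at Week 8/early termination** in both places, and name Week 0 as its baseline to match MADRS. This is preferable if HAM-D is kept. It adds at most 120 ratings at two existing visits. Specify ANCOVA here too, since repeated measures modelling adds nothing with one later value.

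For options 2 and 3, the edit is to insert HAM-D between ASEX and HAM-A in each affected assessment line, and to mark the matching cells in the schedule.

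Two points need a sentence in the plan if HAM-D is kept:

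- **Baseline.** Section V.B has the switch arm taper its SSRI over 2 to 4 weeks after eligibility, while the quetiapine arm continues its antidepressant. If that period falls between screening and Week 0, a change from screening includes it and a change from Week 0 does not. The choice of baseline should be made with this in view.
- **Missing values.** With a single later rating there is nothing to carry forward, so participants who leave without an early termination visit will have no HAM-D outcome. State this, and report the number missing in each arm.

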- Has a disease or takes medication that, in the opinion of the investigator, could interfere with the assessments of safety, tolerability, or efficacy or prevent the individual from completing the study. Female subjects of childbearing potential not on adequate contraception methods in the opinion of the investigator
 - If the female is childbearing, she must agree to use appropriate contraceptive measures for the duration of the study and for one month afterwards. Medically acceptable contraceptives include: (1) surgical sterilization (such as tubal ligation or hysterectomy), (2) approved hormonal contraceptives (such as birth control pills, patches, implants, or injections), (3) barrier methods (such as condom or diaphragm) used with a spermicide, or (4) an intrauterine device (IUD). Contraceptive measures such as Plan B™, sold for emergency use after unprotected sex, are not acceptable methods for routine use. If the female does become pregnant during this study she must inform the study physician immediately.
- Has a significant risk of suicide according to Columbia Suicide Severity Rating Scale (CSSRS) or in the clinical judgment of the investigator
- History of suicide attempt in the previous 12 months
- MDD with postpartum onset, psychotic features or seasonal features
- Hamilton Anxiety Scale (HAM-A) baseline score ≥ 24
- Failure of ≥ 3 adequate trials of different antidepressants for the current episode of MDD
- ≥ 3 episodes major depression in previous 12 months or ≥ 8 lifetime episodes of MDD
- Current or previous use of an atypical or typical antipsychotic agent for augmentation of major depression or treatment of psychotic depression, mania psychosis, or agitation. Previous use of antipsychotics for insomnia will be permitted.

V. STUDY PROCEDURES

A. Blinding and Controls:

The study will be rater blinded, randomized, parallel study. Patients will be randomized in 1:1 ratio to levomilnacipran ER switch arm or adjunctive quetiapine arm. Subjects will be instructed not to discuss any clinical issue with the blinded rater. The blinded rater will be specifically instructed to perform specified ratings only and not to address or ask any other study related questions.

B. Drugs, Dosages, and Regimens:

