Safety and tolerability will be assessed by spontaneously reported adverse events, Columbia Suicide Severity Rating Scale (CSSRS) Arizona Sexual Experience Scale (ASEX) scores, vital signs, weight and BMI measurements and clinical laboratory assessments and evaluating reasons for dropout from the trial.

Adverse event: any untoward medical occurrence associated with the use of a drug in humans, whether or not considered drug related.

Suspected adverse reaction: any adverse event for which there is a reasonable possibility that the drug caused the adverse event

Serious Adverse Event (SAE)

A serious adverse event is one that:

- Results in death
- Is an immediate threat to life?
- Requires inpatient hospitalization, or prolongation of existing hospitalization
- Results in persistent or significant disability/incapacity
- Is a congenital anomaly or birth defect.

Causality Assessment

For all AEs, the Investigator must provide an assessment of causal relationship to the IP.

Causal relationship must be assessed by answering the following question:

Is there a reasonable possibility the IP caused the event?

Yes: There is a possible or probable relationship (i.e., there is a reasonable or strong temporal relationship, and the events are unlikely to be attributable to other drugs, underlying diseases, or other factors). Challenge and/or rechallenge (if available) is positive.

No: The relationship is unlikely or nonexistent (i.e., there is no strong temporal relationship and/or the use of other drugs, underlying diseases, or other factors provide plausible explanations for the event), or the patient did not take the IP.

Reporting of Adverse Events:

All spontaneously reported and observed adverse events will be recorded in the source and CRF documents. The Principal Investigator will inform Actavis/Forest Global Drug Safety of all SAEs within 24 hours of first knowledge of any AE that meets one of the criteria for an SAE, on a SAE report form. If, during follow-up, any nonserious AE worsens and eventually meets the criteria for an SAE, that AE will be recorded as a new SAE.

The study centers will transmit the SAE report form to the SAE [contact]) within 24 hours of first awareness of the event at the study center. Supplemental information will be submitted as soon as available and may include laboratory results,

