radiology reports, progress notes, hospital admission and emergency room notes, holding and observation notes, discharge summaries, autopsy reports, and death certificates.

Reporting of Pregnancy to Allergan, Inc. / Forest Research Institute

Study center personnel will report every pregnancy on a pregnancy report form as soon as possible (within 24 hours of first awareness of the pregnancy to the Allergan, Inc. pregnancy fax number, [contact]), even if no AE has occurred, and follow it to term. If, however, the pregnancy is associated with an SAE (e.g., if the mother is hospitalized for dehydration), in addition to the pregnancy report form, a separate SAE report form will be filed.

Any Serious Adverse Event will also be reported to the Duke IRB, to the FDA within 24 hours. The FDA Adverse Event Reporting System (AERS) is a computerized information database designed to support the FDA's post-marketing safety surveillance program for all approved drug and therapeutic biologic products. The FDA uses AERS to monitor for new adverse events and medication errors that might occur with these marketed products.

VII. STATISTICAL EVALUATION

A. Power analysis:

The proposed design levomilnacipran switch has never previously been studied in either a randomized or open-label design. Thus no direct pilot data exist upon which to base a power analysis. As is recommended for cases where pilot data are absent or minimal, clinical trials can be powered to detect clinically meaningful effect sizes. What is clinically meaningful depends on the illness and outcome being studied. According to mainstream resources, such as British National Institute for Health and Clinical Excellence (NICE), it is generally accepted that small effect sizes are not clinically meaningful, while medium effect sizes are. If one uses standardized effect sizes (Cohen's d) to determine clinical significance, the British National Institute for Health and Clinical Excellence (NICE) has suggested that $d=0.50$ should be the standard general threshold for "clinical significance" in drug treatments (www.nice.org.uk). This standard has been applied to assessing efficacy in RCTs with antidepressants in MDD (Kirsch et al., 2008).

Sample Size calculations for two-sided log rank test in survival analysis

Power	Proportion Response: Drug	Proportion Response: Placebo	Alpha	Number in each group
0.90	.33	.17	0.05	44
0.80	.33	.17	0.05	28
0.90	.45	.27	0.05	48
0.80	.45	.27	0.05	31

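### The SAE definition has no important-medical-event criterion, so some suicide attempts, overdoses and seizures get no 24-hour report; the second site's IRB is also not named to receive SAEs

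*Combined protocol and SAP*

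**What the plan says.** Under Clinical Assessments, Safety/Tolerability, an event is serious if it meets one of five criteria:

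- "Results in death"
- "Is an immediate threat to life"
- "Requires inpatient hospitalization, or prolongation of existing hospitalization"
- "Results in persistent or significant disability/incapacity"
- a congenital anomaly or birth defect

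The list ends there. It has no item for other medically important events and none that rests on the investigator's judgment.

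The paragraph on reporting adverse events requires notice to the manufacturer's drug safety group "within 24 hours of first knowledge of any AE that meets one of the criteria for an SAE, on a SAE report form". After the pregnancy paragraph the protocol adds: "Any Serious Adverse Event will also be reported to the Duke IRB, to the FDA within 24 hours".

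On oversight, section XI.A says that the Duke IRB approves the protocol for the Duke site. The other "site will use an external IRB (e.g. Copernicus, Western) and provide Duke with a copy of its approval". Section IV.A plans 60 subjects at 2 sites, 30 of them at Duke.

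The exclusion criteria (IV.D) include "History of suicide attempt in the previous 12 months" and a history of epilepsy. The visit schedule (XIV) marks the C-SSRS at every visit from screening to week 9.

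**The concern.** Patients in this trial have depression that has not responded adequately to an SSRI. They either taper that drug and start another, or add a second drug to it. A suicidal act that is treated without admission is a foreseeable event in such a population, and the protocol's exclusions and C-SSRS schedule show that its authors had suicidality in mind. The SAE definition does not follow through. For events that fall short of the five outcomes, the seriousness label turns largely on whether the patient was admitted, and the 24-hour reporting duty turns on that label.

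What is at stake is how quickly those outside the study team learn of such an event, and whether the two sites would classify like events alike.

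The IRB question is separate and smaller. The protocol names one IRB as a recipient of SAEs but places its two sites under two IRBs.

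**Working it through.** No sample size, power or alpha figure is involved. The check sets the reporting provisions side by side.

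**Step 1: test an event against the definition.** Take a suicide attempt, overdose or seizure that is treated and sent home, in two versions: A, not immediately life-threatening and not disabling; B, immediately life-threatening.

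| Criterion | A | B |
|---|---|---|
| Death | no | no |
| Immediate threat to life | no | **yes** |
| Admission or prolonged stay | no | no |
| Lasting or significant disability | no | no |
| Birth defect | no | no |
| Criteria met | 0 of 5 | 1 of 5 |

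B is an SAE without admission. A is not an SAE, and nothing in the list lets an investigator make it one.

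**Step 2: follow the reporting duty.** The report to the manufacturer applies to an AE that meets one of the criteria. The IRB and FDA sentence applies to SAEs. Event A triggers neither. The one 24-hour trigger outside the SAE list is pregnancy, which is reportable even without an adverse event. The protocol can therefore set a trigger of its own where it wants one, and it sets none for suicidal acts.

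**Step 3: ask whether another provision fills the gap.**

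- *C-SSRS and the termination rule (V.C).* Worsening at two successive visits, or clinician judgment, ends participation. This is a rule about staying in the trial and creates no report. Visits are two weeks apart between weeks 4, 6 and 8.
- *Weekly calls (V.C, washout and baseline procedures).* They cover suicidal risk, and concerns go to the PI. No report outside the study team is specified.
- *Upgrade rule.* A non-serious AE that later meets the criteria becomes a new SAE. Event A never meets them.
- *Monthly teleconferences (XI.F).* The two sites' PIs review AEs and SAEs, and a concern can lead to urgent communication or a modified protocol. The scheduled interval is a month.

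None of these is expedited reporting.

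**Step 4: compare SAE recipients with IRB coverage.** The protocol names three recipients: the manufacturer's drug safety group, the Duke IRB and the FDA. One of the three is an IRB, and XI.A describes its approval for the Duke site only. Planned enrolment outside Duke is 60 − 30 = 30, which is 30/60 = 50%. For that site the protocol names no SAE report to the reviewing IRB. The paragraph on quality assurance audits, by contrast, refers to the IRBs of the participating sites in the plural.

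**The case against.** The strongest reply is that the gap is narrow and the event is not lost. All spontaneously reported and observed AEs must be recorded, so event A would still be in the source documents and the case report form, and the C-SSRS could capture it as well. The calls, the termination rule and the monthly review give some oversight. All of this stands. It limits the consequence to the seriousness label and the 24-hour report.

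Four stronger readings are tempting, and the documents do not support them.

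- *Every attempt or overdose without admission is non-serious.* The life-threat and disability criteria do not require admission.
- *The Duke IRB is the sole recipient of SAEs.* The manufacturer and the FDA receive them too, and the manufacturer's report comes from the study centers, in the plural. The Duke IRB is only the sole IRB named.
- *The second site's IRB cannot act on that site's SAEs.* The protocol is silent on reports to that IRB and does not forbid them. The sentence naming the Duke IRB is worded as an addition, and the external IRB may have reporting rules of its own that are not in these documents.
- *SAE counts by arm are understated, which distorts the tolerability comparison.* SAE counts are not among the listed safety and tolerability measures. Safety data are summarised descriptively, without formal testing.

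**Conclusion.** The main point holds in bounded form. Followed as written, the protocol leaves a suicide attempt, overdose or seizure that is not immediately life-threatening, not disabling and not admitted without any specified 24-hour report. This rests on reading the five items as a complete list, which is how the reporting trigger uses them. No event rate is given, so the number of patients affected cannot be estimated; it could be zero.

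The IRB point also holds, but mainly as an omission. About half of planned enrolment, 30 of 60, falls under an IRB that the protocol does not name as an SAE recipient. That figure is planned enrolment and says nothing about the number of unreported events.

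A reader might further infer that every attempt, overdose or seizure should be an SAE automatically. The documents do not support such a blanket rule; a criterion that rests on judgment is enough to close the gap. Neither point touches the primary endpoint, the sample size or the efficacy analysis. Both should be corrected because they concern patient safety and are cheap to fix.

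**What to change.** 1. Add a sixth criterion to the SAE definition and the SAE form: an important medical event that, in the investigator's judgment, may jeopardise the patient or require intervention to prevent one of the listed outcomes.
2. State that suicide attempts, overdoses and seizures without admission are assessed against this criterion, at both sites.
3. In the sentence on reporting SAEs to the IRB and the FDA, replace the single named IRB with each site's IRB of record. Keep the report to the Duke IRB if it is meant to see SAEs from both sites, and say so.

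The cost is two or three sentences in the protocol and a change to the form. The downside is a few more expedited reports.
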